9 CROSSOVER PERIOD

9.1 Crossover Period Design

After completing the randomized period, subjects that have confirmed skin disease progression on the vorinostat arm can be assessed for eligibility for the crossover period. Eligible subjects may elect to enter this optional crossover period and must have signed a study informed consent form (corresponding to the current version of the SOLAR protocol) to proceed. Every effort will be made to perform final safety and disease assessments for subjects who withdraw from the study early.

Potential subjects will need to complete the crossover screening activities and meet the entry criteria (see [Section 5.2](#)) prior to enrollment into the crossover period.

Subjects in the randomized period of the study who withdrew consent **without confirmation of skin disease progression** are not eligible to enroll in this period. In addition, subjects who received any subsequent systemic therapy for MF following confirmed disease progression in the randomized period are not eligible for the crossover period.

Study procedures completed at the End of Treatment visit in the randomized period may be used for screening assessments in the crossover period, depending on the timing of the assessments. Subjects who initiate Screening in the crossover period > 28 days after completing the randomized period will need to complete all of the crossover Screening procedures.

Subjects will undergo Screening lasting up to 28 days from the time of the first screening procedure, followed by active treatment and follow-up for response and disease progression.

Subjects who are currently on active treatment in the **PRISM Study (MRG106-11-203)** may enter the crossover period of this protocol, once the site has received necessary IRB/IEC and regulatory approvals for the current version of the SOLAR protocol. In this case, site personnel will ensure the subject has provided written informed consent for the SOLAR crossover period. The subject will not need to be re-evaluated for the entry criteria for SOLAR crossover period and should enter the study at the next scheduled nominal study visit following the last study visit completed in the PRISM study.

9.2 Crossover Study Schedule

Before recruitment of subjects into the crossover period, written Institutional Review Board/Independent Ethics Committee (IRB/IEC) approval of the protocol, informed consent and any additional subject information must be obtained.

The required visits for the crossover period are listed below. The investigator can bring the subject into the clinic for an unscheduled visit at any time.

9.2.1 Crossover Screening Period (Day -28 to Day -1)

All Screening procedures to determine eligibility must be performed within the specific time windows. Eligibility is determined by results of the assessments performed prior to enrollment. Disease staging and eligibility will be confirmed by the Medical Monitor prior to enrollment (24-48 hours should be allowed for Medical Monitor review).

Subjects may be rescreened once at the discretion of the Investigator (i.e., if a subject does not meet the Inclusion/Exclusion criteria during the first Screening assessments). Individual Screening assessments may be repeated, if the subject is still within the 28-day Screening window. If a subject is outside of the 28-day Screening window, then the subject must be reconsented and all Screening procedures should be repeated. If an assessment is repeated, the result obtained closest to enrollment should be used for eligibility.

Screening may last up to 28 days from the time the first study screening procedure is completed.

During Screening, the IWRS will assign a unique subject identification number to each subject who signs informed consent for the study. Once a subject is in Screening or is enrolled into the study, s/he will only be identified by the assigned identification number throughout the crossover period.

The Investigator or designee is responsible for verifying that a subject is eligible before initiating the enrollment. Eligibility must also be confirmed by the Medical Monitor, prior to enrollment. Subjects must be treated within 3 working days of the date of enrollment.

Prior to performing study related procedures:

- Verify informed consent (including crossover procedures) of potential subject by written signature on an ICF.

From Days -28 to -3, the following evaluations will occur:

- Register the subject in the IWRS.
- Obtain vital signs (blood pressure, heart rate, respiratory rate, and body temperature) (if not obtained within 14 days prior to Day 1).
- Perform MF disease evaluation using the mSWAT (if not done within 28 days prior to Day 1) (see [Appendix F](#)).

- Record prior and concomitant medications administered from 30 days prior to the first dose of study treatment.
- Record any new MF treatments following discontinuation of vorinostat in the randomized period.
- Record ECOG performance status.
- Perform a complete physical examination (including documentation of height and weight) (if not done within 14 days prior to Day 1)
- Perform a triplicate 12-lead ECG (if not done within 14 days of Day 1).
- Collect blood for the following central laboratory analysis (if not done within 14 days of Day 1):
 - FSH (for females who are not surgically sterile as confirmation of menopause for females who last menstrual cycle was within the last year)
 - Serum pregnancy test (for females of childbearing potential);
 - Hematology;
 - Clinical chemistry;
 - TSH;
 - Coagulation.
- Collect blood for flow cytometry and a concomitant CBC (performed locally; panels must include antibodies to CD3, CD4, CD8, CD26, CD45 and CD7) (if not done within 28 days of Day 1).
- Collect urine for central laboratory analysis of urinalysis (with microscopy) (if not done within 14 days of Day 1).
- Review eligibility of medical history and laboratory measurements according to inclusion/exclusion criteria.
- Review and record AEs.

From Days -3 to -1, the following evaluations will occur:

- Confirm eligibility of medical history and laboratory measurements according to inclusion/exclusion criteria.
- Re-review and record AEs.

- Enter all Screening data in the eCRF and initiate Medical Monitor review in the IWRS (allow 24-48 for Medical Monitor review).

9.2.2 Crossover Active Treatment

Subjects will be monitored and treated in the outpatient setting. After all dosing and study procedures are completed at each study visit, subjects will return home until the next visit.

9.2.2.1 Day 1 (First Day of Study Treatment)

- Perform CTCL disease evaluation using the mSWAT (predose) (see [Appendix F](#)).
- Obtain predose vital signs (blood pressure, heart rate, respiratory rate, and body temperature).
- Perform a complete physical examination (including documentation of weight). This examination may be performed within 2 days prior to the Day 1 visit.
- Collect blood for the following:
 - Complement C5a, Bb testing (predose and within the 10 minutes before the end of the infusion);
 - Hematology (predose; only if Screening measurement was performed > 3 days before Day 1);
 - Clinical chemistry (predose; only if Screening measurement was performed > 3 days before Day 1);
 - TSH (predose; only if Screening measurement was performed > 3 days before Day 1);
 - Coagulation (predose and at 3 hours [\pm 10 minutes] postdose);
 - PD and ADA (predose);
 - PK (predose, and 5 ± 5 minutes before the end of the infusion).
- Collect urine for the following:
 - Urinalysis (predose; only if Screening measurement was performed > 3 days before Day 1);
 - Pregnancy test (predose, for females of childbearing potential).

- Perform a single 12-lead ECG (predose and as soon as possible postdose, ideally within 30 minutes of the end of infusion).
- IWRS transaction (cobomarsen dispensation).
- Administer intravenous infusion of cobomarsen with vital signs performed within 15 minutes of the end of the infusion. Monitor subject in the clinic for safety for a minimum of 4 hours postdose.
- Review and record AEs and concomitant medications.

9.2.2.2 Day 2

- Obtain vital signs (blood pressure, heart rate, respiratory rate, and body temperature).
- Collect blood for the following:
 - Complement C5a, Bb testing (24 ± 4 hours after Day 1 dosing);
 - Coagulation;
- Review and record AEs and concomitant medications.

9.2.2.3 Day 3 (+ 1 Day)

- Obtain predose vital signs (blood pressure, heart rate, respiratory rate, and body temperature).
- Collect blood for the following:
 - Hematology (predose);
 - Clinical chemistry (predose);
 - TSH (predose);
- Collect urine for urinalysis (predose).
- IWRS transaction (cobomarsen dispensation).
- Administer intravenous infusion of cobomarsen with vital signs performed within 15 minutes of the end of the infusion.
- Review and record AEs and concomitant medications.

9.2.2.4 Day 5 (± 1 Day)

- Obtain predose vital signs (blood pressure, heart rate, respiratory rate, and body temperature).
- IWRS transaction (cobomarsen dispensation).
- Administer intravenous infusion of cobomarsen with vital signs performed within 15 minutes of the end of the infusion.
- Review and record AEs and concomitant medications.

9.2.2.5 Day 8 (± 1 Day)

- Obtain vital signs (blood pressure, heart rate, respiratory rate, and body temperature).
- Perform a brief, symptom-directed physical examination.
- Collect blood for the following:
 - Hematology (predose);
 - Clinical chemistry (predose);
 - TSH (predose);
 - Coagulation (predose);
- Collect urine for urinalysis (predose).
- IWRS transaction (cobomarsen dispensation).
- Administer intravenous infusion of cobomarsen with vital signs performed within 15 minutes of the end of the infusion.
- Review and record AEs and concomitant medications.

9.2.2.6 Day 15 (± 1 Day)

- Obtain predose vital signs (blood pressure, heart rate, respiratory rate, and body temperature).
- Perform a brief, symptom-directed physical examination.
- Collect blood for the following:
 - Hematology (predose);
 - Clinical chemistry (predose);

- TSH (predose);
- PD and ADA (predose).
- Collect urine for urinalysis (predose).
- IWRS transaction (cobomarsen dispensation).
- Administer intravenous infusion of cobomarsen with vital signs performed within 15 minutes of the end of the infusion.
- Review and record AEs and concomitant medications.

9.2.2.7 Day 22 (± 2 Days)

- Obtain predose vital signs (blood pressure, heart rate, respiratory rate, and body temperature).
- IWRS transaction (cobomarsen dispensation).
- Administer intravenous infusion of cobomarsen with vital signs performed within 15 minutes of the end of the infusion.
- Review and record AEs and concomitant medications.

9.2.2.8 Day 29 (± 3 Days)

- Perform CTCL disease evaluation using the mSWAT (predose) (see [Appendix F](#)).
- Obtain predose vital signs (blood pressure, heart rate, respiratory rate, and body temperature).
- Perform a brief, symptom-directed physical examination (including documentation of weight).
- Collect blood for the following:
 - Hematology (predose);
 - Clinical chemistry (predose);
 - TSH (predose);
 - Coagulation (predose);
 - PD and ADA (predose);
 - PK (predose, and 5 ± 5 minutes before the end of the infusion).

- Collect urine for the following:
 - Urinalysis (predose);
 - Pregnancy test (for females of childbearing potential).
- Perform a single 12-lead ECG (predose and as soon as possible postdose, ideally within 30 minutes of the end of infusion).
- IWRS transaction (cobomarsen dispensation).
- Administer intravenous infusion of cobomarsen with vital signs performed within 15 minutes of the end of the infusion.
- Review and record AEs and concomitant medications.

9.2.2.9 Weekly Assessments Starting at Week 6 (\pm 3 Days)

Starting at Week 6, the following assessments are required to be done weekly.

- Obtain predose vital signs (blood pressure, heart rate, respiratory rate, and body temperature).
- IWRS transaction (cobomarsen dispensation).
- Administer intravenous infusion of cobomarsen with vital signs performed within 15 minutes of the end of the infusion.
- Review and record AEs and concomitant medications.

9.2.2.10 Every-4-Week Assessments from Weeks 9 through 81, then Every-8-Week Assessments Thereafter (\pm 3 Days)

NOTE: In addition to the weekly assessments listed above, the following additional assessments are required to be done every 4 weeks from Week 9 through Week 81 and then every 8 weeks thereafter:

- Perform CTCL disease evaluation using the mSWAT (predose) (see [Appendix F](#)).
- Perform a brief, symptom-directed physical examination (including documentation of weight).
- Collect blood for the following:
 - Hematology (predose);
 - Clinical chemistry (predose);

- TSH (predose);
- PD and ADA (predose);
- PK (predose only through Week 81, and every 8 weeks thereafter).
- Collect urine for the following:
 - Urinalysis (predose);
 - Pregnancy test (performed every 4 weeks while on study treatment), for females of childbearing potential.
- Perform a single 12-lead ECG (predose).
- Review and record AEs and concomitant medications.

9.2.3 End of Treatment Visit

At the time of study treatment discontinuation, the End of Treatment Visit should be completed for all subjects after the last dose of study treatment, and every effort should be made to perform the procedures listed below. This visit should take place as soon as possible and ≤ 14 days after the last dose of study treatment. The date and reason for stopping the study treatment will be reported. The End of Treatment visit is not considered as the end of the study. All subjects will enter Follow-up unless they have withdrawn their consent to do so.

- Perform CTCL disease evaluation using the mSWAT (see [Appendix F](#)).
- Obtain vital signs (blood pressure, heart rate, respiratory rate, and body temperature).
- Perform a brief, symptom-directed physical examination (including documentation of weight).
- Collect blood for the following:
 - Hematology;
 - Clinical chemistry;
 - TSH;
 - PD and ADA
 - PK.
- Collect urine for the following:
 - Urinalysis;

- Pregnancy test (for females of childbearing potential).
- Perform a single 12-lead ECG.
- IWRS transaction (discontinue the subject in the system).
- Review and record AEs and concomitant medications.

9.3 Long-term Follow-up for Subjects Who Have Not Progressed at the Time of End of Treatment Visit

After the End of Treatment Visit, subjects who did not progress on study will be followed until progression (confirmed progression in skin, confirmed loss of response in skin or clinical progression in lymph nodes, blood or viscera assessed per investigator discretion), withdrawal of consent, initiation of subsequent MF treatment, loss to follow-up, or death, and the subject's final disposition is documented and reviewed by the Sponsor study team.

9.3.1 Every-4-Week Assessment through Week 81, then Every-8-Week Assessments Thereafter (± 3 Days)

- Perform CTCL disease evaluation using the mSWAT (see [Appendix F](#)).
- Review and record AEs and concomitant medications.

9.3.2 Follow-up Visit 28 ± 5 days after the End of Treatment or Early Termination

For subjects who discontinue treatment, the following assessments will be performed 28 ± 5 days after the End of Treatment Visit (assuming the subject has not withdrawn consent).

- Perform CTCL disease evaluation using the mSWAT (does not need to be repeated if disease progression is already confirmed) (see [Appendix F](#)).
- Obtain vital signs (blood pressure, heart rate, respiratory rate, and body temperature).
- Perform a brief, symptom-directed physical examination (including documentation of weight).
- Collect blood for the following:
 - Hematology;
 - Clinical chemistry;
 - TSH;
 - Coagulation;

- PD and ADA
- PK.
- Collect urine for the following:
 - Urinalysis;
 - Pregnancy test (for females of childbearing potential).
- Perform a single 12-lead ECG.

Review and record AEs and concomitant medications.

10 ASSESSMENT OF SAFETY

10.1 Specification of Safety Parameters

Safety will be evaluated through continuous monitoring of AEs, vital signs, physical examinations, clinical laboratory measurements, and ECGs.

Management of Infusion-related adverse events:

Allergic events and/or infusion-related toxicities should be managed according to institutional guidelines. If institutional guidelines are not available, the following recommendations apply.

Rash, pruritus, urticaria and wheezing due to an infusion-related AE, may be treated with diphenhydramine hydrochloride and/or steroids as clinically appropriate. Anaphylaxis or anaphylactoid signs or symptoms may be treated with steroids and/or epinephrine as clinically indicated. Any concomitant therapies used must be recorded in the eCRF. The Medical Monitor should be consulted prior to the use of steroids whenever possible. Subjects should be treated in a facility equipped for cardiopulmonary resuscitation. Infusion-related reactions (fever, rigors) should be treated per institutional guidelines but may be treated with acetaminophen and diphenhydramine hydrochloride.

10.2 Dose Modifications Interruptions and Stopping Rules

More than 4 missed consecutive doses of cobomarsen, or a dose interruption of > 14 consecutive days of vorinostat, due to an AE or clinically significant laboratory abnormality, or other significant noncompliance with study treatment administration should result in permanent discontinuation of study treatment, unless it is judged by the Investigator and Sponsor Medical Monitor or designee to be in the best interest of the subject to continue treatment. Regardless of

study treatment administration, subjects should continue to follow the study procedure schedule outlined in [Section 8](#) and [Section 9](#).

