3.2.2 Secondary Endpoints

Efficacy measures:

- Progression-free survival (PFS).
- Complete response rate (CRR).
- Time to progression (TTP).
- Time to maximal effect in skin (mSWAT).
- Proportion of subjects achieving $\geq 50\%$ improvement in mSWAT of at least 28-days duration (ORR1).
- Proportion of subjects achieving $\geq 50\%$ improvement in mSWAT from baseline at 28 days and at 4 months.
- Time to $\geq 50\%$ improvement in mSWAT.
- Duration of response in skin (no progression after achieving $\geq 50\%$ improvement in mSWAT).
- Change in pruritus medication utilization from baseline and incidence of pruritus medication utilization.

- During the crossover portion of the study:
 - Proportion of subjects achieving an objective skin response (complete response [CR] or partial response [PR]) of at least 4 months duration (ORR4) using the mSWAT scoring (see [Appendix F](#)).
 - Progression-free survival (PFS).
 - Complete response rate (CRR)
 - Time to progression (TTP).
 - Time to maximal effect in skin (mSWAT).
 - Proportion of subjects achieving $\geq 50\%$ improvement in mSWAT of at least 28-days duration (ORR1).
 - Proportion of subjects achieving $\geq 50\%$ improvement in mSWAT from baseline at 28 days and at 4 months.
 - Time to $\geq 50\%$ improvement in mSWAT.
 - Duration of response in skin (no progression after achieving $\geq 50\%$ improvement in mSWAT).
 - Change in pruritus medication utilization from baseline and incidence of pruritus medication utilization.

Safety and Tolerability Evaluations:

- Incidence and severity of clinically significant AEs (including grade 3 and 4 AEs, treatment-related AEs, SAEs, and AEs requiring discontinuation), physical examination findings, changes in electrocardiogram (ECGs), changes in laboratory parameters and changes in vital signs.
- Characterization of anti-drug antibody generation.

Pharmacokinetic Evaluation:

- Population PK parameters.
- During the crossover portion of the study
 - Pharmacokinetic C_{\max} and trough concentration analysis

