5.4 Subject Discontinuation or Withdrawal from Study

5.4.1 Reasons for Subject Discontinuation or Withdrawal of Consent

Subjects may withdraw their consent to participate in the study at any time for any reason without prejudice to their future medical care by the physician or at the institution. If a subject withdraws consent, the date and reason for consent withdrawal should be documented. The clinical site staff will also need to document from what portion of the study the subject is withdrawing consent:

1. Withdrawing from treatment, but will continue to be followed for safety and progression;
2. Withdrawing from treatment and all study procedures, but agrees to complete End of Treatment and 28 day post treatment follow-up visit;
3. Complete study withdrawal with no additional follow-up.

Subjects meeting any of the following criteria should discontinue study treatment:

- Unacceptable AE(s) or failure to tolerate study treatment (see [Section 10.2](#));
- Prolonged dose delay (i.e., more than 4 missed consecutive doses of cobomarsen, or a dose interruption of > 14 consecutive days of vorinostat), due to an AE or clinically significant laboratory abnormality, or significant noncompliance with study treatment administration, unless judged by the Investigator and Sponsor Medical Monitor or designee to be in the best interest of the subject to continue treatment;
- Changes in the subject's condition or development of an intercurrent illness that renders the subject unsuitable for further study treatment in the judgment of the Investigator;
- Disease progression (see [Section 4](#));
- Initiation of non-protocol CTCL treatment;
- Withdrawal of consent;
- Pregnancy;
- Subject is lost to follow-up;
- Discretion of the Investigator;

- Termination of the study by the Sponsor.

Subjects meeting any of the following criteria should discontinue follow-up for disease progression:

- Confirmed disease progression (see [Section 4](#));
- Withdrawal of consent;
- Initiation of a subsequent CTCL treatment;
- Subject is lost to follow-up;
- Death.

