6.2 Dosage, Preparation and Administration of Study Products

6.2.1 Dose and Regimen, Randomized Period

As outlined in [Section 4.3](#), the following study treatments will be administered according to randomized treatment assignment (cobomarsen or vorinostat):

- Cobomarsen will be administered by 2-hour intravenous infusion at a dose of 282 mg on Days 1, 3, 5, 8, and weekly thereafter;
- Vorinostat will be administered orally at a dose of 400 mg (four 100 mg capsules) once daily with food, at approximately the same time each day.
 - Subjects assigned to vorinostat with abnormal ALT/AST (> ULN) or bilirubin (> 1.0 × ULN) at Screening will start vorinostat dosing at 300 mg (three 100 mg capsules) once daily with food, at approximately the same time each day, per dosing guidelines.

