12.4.5 Safety Analyses

Treatment-emergent AEs will be coded by preferred term and system organ class using the Medical Dictionary for Regulatory Activities (MedDRA[®]) and summary tables for all AEs will be generated for the Safety Population. Incidence rates and percentages will be summarized by preferred term and system organ class. Additional summary tables will be generated for the following population subsets: subjects with SAEs, subjects with treatment related AEs, subjects who discontinue due to AEs, and subjects with grade 3 or 4 AEs. Severity will be assessed according to the NCI CTCAE version 5.0 and relationship to study treatment will be attributed by investigator.

Concomitant medications will be coded using the World Health Organization Drug Dictionary (WHO-DD; March 2015 or later version). A dictionary listing of all unique concomitant medications used in the study will be provided.

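### The AE-hold limit is about twice as long in calendar time for cobomarsen as for vorinostat, and the planned AE-discontinuation table cannot separate this rule's effect from toxicity

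*Combined protocol and SAP*

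**What the plan says.** Section 10.2 sets the limit as "More than 4 missed consecutive doses of cobomarsen, or a dose interruption of > 14 consecutive" days of vorinostat. It applies when the delay is due to an AE or a clinically significant laboratory abnormality, or to other significant noncompliance. Treatment should then stop permanently unless the Investigator and the Sponsor Medical Monitor (or designee) judge that continuing is in the subject's best interest. Section 5.4.1 repeats both limits ("more than 4 missed consecutive doses of cobomarsen" and "a dose interruption of > 14 consecutive days of vorinostat") under a prolonged-delay reason, listed apart from stopping for unacceptable AEs or intolerance.

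The dosing intervals are in Section 6.2.1: "Cobomarsen will be administered by 2-hour intravenous infusion at a dose of 282 mg on Days 1, 3, 5, 8, and weekly thereafter", and "Vorinostat will be administered orally at a dose of 400 mg (four 100 mg capsules) once daily with food".

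Section 3.2.2 lists as a safety endpoint "Incidence and severity of clinically significant AEs (including grade 3 and 4 AEs, treatment-related AEs, SAEs, and AEs requiring discontinuation", among other items. Section 12.4.5 plans summary tables that include subjects "who discontinue due to AEs, and subjects with grade 3 or 4 AEs". Sections 12.4.5 to 12.4.5.3 plan no table of AE-related interruptions or their length. Nothing in the protocol gives a reason for the different calendar limits, or says whether a prolonged-delay stop caused by an AE is tabulated as an AE discontinuation.

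**The concern.** One limit is counted in doses and the other in days, and the two drugs have different dosing intervals. For clinically significant grade 3/4 AEs, Sections 10.2.1 and 10.2.2 handle the hold in nearly the same way: delay, give supportive care, resume on resolution or return to baseline. The same AE can therefore start the same kind of hold in both arms, yet that hold is timed against different clocks.

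The interpretation of a listed tolerability endpoint is at stake. If the arms differ in AE discontinuations, a reader of the planned tables could not tell how much reflects the drugs and how much reflects the hold limit.

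**Working it through.** The documents state no derived figure for the hold limits, so there is nothing to reproduce. The check converts both limits to calendar days.

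**Inputs.** Limits from 5.4.1 and 10.2; dosing days from 6.2.1; 63 subjects per arm from 12.5.1. AE durations and the share of subjects with a hold are not in the documents and are assumed below.

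**1. Weekly phase (last cobomarsen dose on Day 8 or later).**
- Cobomarsen infusions fall due 7, 14, 21, 28 and 35 days after the last one. More than 4 missed means the fifth, on day 35. That is 35 − 7 = 28 days after the first missed due date.
- Vorinostat: more than 14 days means the fifteenth missed daily dose, on day 15 after the last dose, 14 days after the first missed one.
- Permitted missed dosing: 4 × 7 = 28 days against 14, ratio 2.0. Trigger after last dose: 35/15 = 2.3.

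**2. Cobomarsen loading phase.**

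| Last dose | Five missed doses (study days) | Days after last dose | Days after first missed dose | Ratio to vorinostat (÷15) |
|---|---|---|---|---|
| Day 1 | 3, 5, 8, 15, 22 | 21 | 19 | 1.4 |
| Day 3 | 5, 8, 15, 22, 29 | 26 | 24 | 1.7 |
| Day 5 | 8, 15, 22, 29, 36 | 31 | 28 | 2.1 |

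**3. Which AEs are treated differently (weekly phase).** Let the AE prevent dosing for D days from onset, with onset uniform in the dosing week. Vorinostat reaches its limit if D > 14. Cobomarsen reaches it with probability min(1, max(0, (D − 28)/7)).
- D up to 14: neither arm.
- D = 15 to 28: vorinostat only.
- D = 29 to 34: vorinostat always; cobomarsen with probability 1/7 = 0.14 rising to 6/7 = 0.86.
- D of 35 or more: both arms.

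**4. Illustration of size.** Assume the same exponential AE duration (mean m days) in both arms, no override and no dose reduction. An exponential duration has no memory, so once a dose has been missed the remaining time is again exponential with mean m. Given a hold, P(limit reached) = exp(−14/m) on vorinostat and exp(−28/m) on cobomarsen.

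| m (days) | Vorinostat | Cobomarsen | Ratio | Difference |
|---|---|---|---|---|
| 7 | 13.5% | 1.8% | 7.4 | 11.7 points |
| 14 | 36.8% | 13.5% | 2.7 | 23.3 points |
| 28 | 60.7% | 36.8% | 1.65 | 23.9 points |

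These are probabilities per hold. On weekly dosing an AE can resolve before the next infusion is due and cause no hold, so a figure per AE would be lower for cobomarsen (10.7% at m = 14) and is a different quantity.

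If 20% of 63 subjects per arm (12.6) have one hold with m = 14, the limit is reached by 12.6 × 0.368 = 4.6 on vorinostat and 12.6 × 0.135 = 1.7 on cobomarsen. With 10% to 30% having a hold and the three means above, the excess on vorinostat runs from 6.3 × 0.117 = 0.7 to 18.9 × 0.239 = 4.5 subjects.

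**The case against.** A reader might infer that the AE-discontinuation comparison is biased in favour of cobomarsen, so that identical toxicity would show more stops on vorinostat. The documents do not support this, because the hold limit is only one of several stopping rules that differ by arm.
- Towards more cobomarsen stops: no dose reductions; a permanent stop when a grade 2 renal AE of interest recurs; an immediate stop for a grade 4 AE felt to be life-threatening; stops for grade 4 and recurrent grade 3 infusion reactions (10.2.1). Vorinostat's two reduction steps (10.2.2) may also avert long holds.
- Towards more vorinostat stops: the QTc rule above 500 msec (10.2.2), besides the hold limit itself.

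The net direction depends on event rates and hold durations that the documents do not give.

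It is also tempting to say that every rule-driven stop counts as an AE discontinuation. Section 5.4.1 lists prolonged delay as a separate reason, so the classification is undefined. Nor is the stop automatic: the override applies in both arms. It has no stated criteria and is used open-label, so it cannot be relied on to equalise the arms, but the illustration ignores it and is to that extent an upper reading.

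The cobomarsen terminal half-life of about 2.5 to 3 weeks (2.1.3.2) may bear on the longer limit, although the protocol does not say so. Finally, the endpoint is descriptive, is shown beside SAE, treatment-related and grade 3/4 tables, and details are left to an SAP still to be completed (12.1).

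All of this stands against a claim of net bias. None of it removes the unequal clocks or supplies the missing tabulation.

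**Conclusion.** The point holds in a limited form. In the weekly phase the AE-hold limit is 2.0 to 2.3 times as long in calendar time for cobomarsen, with no stated rationale; in the loading phase the ratio is 1.4 to 2.1. AEs that prevent dosing for about 15 to 34 days are the ones treated differently. For any duration distribution with weight in that range, this rule taken alone pushes AE-related stops towards vorinostat. The percentages and counts above are illustrations resting on equal exponential durations, no override and an assumed share of subjects with a hold.

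The consequence is confined to reading a secondary, descriptive safety endpoint. ORR4, PFS, alpha and power are untouched. It is a worthwhile and cheap improvement to the analysis plan, not a defect in the primary analysis. Whether either limit is clinically appropriate is not judged here.

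**What to change.** Leave the clinical rules unchanged. In Section 12.4.5 or the SAP:

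1. Class stops under the prolonged-delay rule that are due to an AE as AE discontinuations, and flag them. Stops for noncompliance stay outside this class.
2. Show AE discontinuations by arm with and without stops due solely to the hold limit.
3. Add a supplementary table of AE-related holds by arm on a common calendar-day scale, measured from the first missed scheduled dose so that it also works in the cobomarsen loading phase. Include the number of subjects with either an AE stop or an AE hold longer than 14 days.

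The table needs an allowance for the ±3-day visit window (8.2.9). Cobomarsen normally resumes at a weekly visit, so a nominal 14-day hold could run to 17 days and be counted as longer than 14 only because the visit was late. On nominal days in the weekly phase, both arms are asked the same question: is dosing still held 14 days after the first missed dose?

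Present this alongside the actual AE-discontinuation count, not in place of it.

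The cost is one derived variable and one or two tables. Infusion times (6.2.4) and vorinostat diaries (6.2.5) give the dosing dates. Neither section says that the reason for a missed dose is recorded, so the eCRF should be checked for this. The resulting tolerability figure may be less favourable to cobomarsen.
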